## **Participatory health technology**

The auto-monitoring application is named “Sleep Well”. The application communicates with a data cluster located in Iceland. The Sleep Well application contains a sleep diary. The diary is inspired by the consensus sleep diary developed by Carney and co-workers (appendix 1). Subjective, quantitative sleep data including sleep efficiency will be calculated based on the formulas proposed by Reed and co-workers. Exercises will be reported in an exercise diary in the sleep well application. A simple question for each of the three daily exercises will be delivered. Adherence to exercises will be assessed by the number of entries to the three daily questions. Administrative co-ordinators will support participants with technical issues.

### *Patient reported outcomes (PROMs) delivered by the “Sleep Well” application*

The European sleep questionnaire is being developed in the Sleep Revolution project. A prototype of the questionnaire has been uploaded as a separate attachment.

### *Neuropsychological tests delivered by the “Sleep Well” application*

Within the SleepWell application there are four cognitive tests which combined cover the major cognitive domains which are affected by sleep disorders. The data from these, will be in the same manner as other data from the SleepWell app, be transferred to the Sleep Revolution data storage within Reykjavik University in Iceland. The four cognitive tests are: i) Inspection Time Test; ii) Psychomotor Vigilance Test; iii) Corsi Block Test, and; iv) Stroop Test. In the following, we will go through each to provide a short overview of its purpose.

#### *Inspection Time Test*

The Inspection Time Test is another neuropsychological test to measure processing speed, perceptual speed, and selective attention. As this test is independent of motor speed, it is therefore applicable for testing participants with motor impairment. In the Inspection Time Test, the participant is presented with a stimulus with a long and short arm. Stimulus presentation duration is varying across trials. After every stimulus presentation, the stimulus is covered by a mask,

and the participant has to decide whether the short arm was on the left or right sight by pressing the corresponding response keys. The participant is instructed that the reaction time does not matter. This test is successfully and widely used.

### Psychomotor Vigilance Test

This tests measures vigilance. Participants are instructed to press a key as soon as the target appears on the screen and get feedback about their reaction time or an error message if an invalid response was given. Vigilance is one of the most affected domains by sleep disorders indicated by a large effect size. Further, impaired vigilance leads to impaired executive control. The Psychomotor Vigilance test is one of the most sensitive measurements for the impact of sleep deprivation on neurocognitive functioning. This test is presented within the app.

### Corsi Block Test

The Corsi Block tests are measurements of executive functions, more precisely working memory. The participant is presented with 9 boxes, which light up in specific sequence. Participants are asked to repeat the sequence. The test starts with 2 boxes and constantly increases the number of boxes. The participant has 2 chances for each sequence length. If one of the sequences was entered correctly, the next sequence is presented. If both of the sequences were entered incorrectly, the experiment ends. In the forward version, the sequence has to be repeated in the exact same order as presented. In the backwards version, the sequence is to be repeated in the reversed order. The Corsi Block tests are one of the most frequently used tests for evaluating the impact of sleep disorders on working memory and are therefore studied intensely in research on working memory. This test is presented in the app.

### Stroop test

The Stroop test is a frequently used test for measuring inhibitory control, selective attention, and cognitive flexibility. It requires the subject to inhibit an unwanted response, and direct the attention to the task-specific goal. The test consists of three parts: In the first part, the subject is asked to read the words "green", "red", "blue", and "yellow" and the reading speed is measured. In the second round, the

colors are presented as blocks and the participant needs to name the correct color. In the last part, a color word is presented in another color, creating an incongruent condition. Here, the participant is instructed to name the color of the word and suppress naming the written word. Reliability and validity of this test are good. In the context of sleep disorders, the Stroop test showed worse performance in patients with OSA and insomnia and is therefore a good addition to this study. This test will be available in the app.

The completion of the tests will be voluntary in this study. Participants will be asked to perform the tests three times during the 90 day study period.

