## **3.0 Material and methods**

**The study is a single blinded RCT with blinded outcome evaluation and intention to treat analysis.** The participants will know by default if they are allocated to the OMTa or waiting list with auto-monitoring during the 90-day intervention period. Blinded baseline- and outcome assessments will be performed by one doctor ([name]) in Norway and one doctor ([name]) in Estonia.

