### ***3.2 Methods***

#### **Prior to the baseline consultation**

All participants will receive a standardized information sheet with login information to the electronic sleep diary. Support on using the application prior to the baseline evaluation will be available by the study co-ordinators by telephone. Evaluation of exclusion criteria will be assessed prior to- or at the baseline study visit. Excluded patients will be referred back to clinical care. Signed informed consent will be obtained and archived on paper.

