### **Baseline evaluation**

Eligible candidates completing auto-monitoring less than 70% of the days prior to baseline assessment will be excluded (see exclusion criteria above). Questions related to the “Sleep Well” application will be answered. [name] and [name] respectively will also ensure that at least 40 of 100 participants are female. After final inclusion, [name] and [name] respectively will schedule the sleep registration and an outcome evaluation session 90 days later. All data collected during the baseline evaluation will be collected in the “Redcap” case report form (CRF).

Further, clinical evaluation will consist of height, weight, standardized blood pressure and a breath holding test. Digital oral scanning will be obtained at both sites. Thereafter, the quantitative scores (OMES) for assessing the myofunctional therapy will be performed and video filmed with one front camera and one camera with a 45-degree angle on the face. The purpose of the video filming is inter rater reliability analyses. All participants will be placed in a chair without arm- or backrest. Body posture on the chair will not be corrected. The baseline assessment will last approximately 90 minutes.

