#### **Randomization**

At the end of the baseline consultation participants will be randomized to either OMTa or only auto-monitoring. Block-randomization with 10 lots per block, per study site, and a 50/50 allocation ratio will be used for waiting list and intervention and separated by sex in order to monitor the 40/60 gender balance. The lots will be made as a code on paper and concealed in opaque envelopes at each study centre. Each participant will also receive a unique e-mail address and a password in the same envelope. The randomization envelopes will be made and mixed by dr. [name]. Envelopes will be sent to dr [name] in Estonia. Both researchers will be blinded for the content in the envelopes.

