## **Outcome evaluation**

At outcome evaluation (estimated time 60 minutes), [name] (Norway) and dr. [name] (Estonia) will repeat the following assessment from the baseline evaluation: A clinical evaluation will consist of height, weight and standardized blood pressure. Thereafter, the quantitative scores (OMES) for assessing the myofunctional therapy and patient reported outcomes will be repeated (see above). Finally additional repeated diagnostics with the hand dynamometer, chewing test and IOPI will be repeated. All data will be collected in the “Redcap” CRF.

Finally, each participants will be given a maximum of five feedback questions. The exact phrasing of the questions will be finalized when answers to similar questions in a pilot study have been analysed. The brief interview will be audio taped and transcribed.

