## **Outcomes**

The primary end point of the RCT is change in the AHI

Secondary endpoints:

1. Change in the Epworth Sleepiness scale and PROMs in the European Sleep Questionnaire.
2. OMTa adherence
3. Change in other conventional OSA severity indices (oxygen desaturation index, time below 90% saturation, nadir saturation) and change in novel OSA parameters in SAS identified in the development phase of the project.
4. Change in objective and subjective sleep quality (PSG and sleep diary, respectively).
5. Change in physiological parameters assessed by wearables.
6. Change in objective daytime functioning testing (PVT and Stroop test).
7. Change in self-reported self-efficacy as assessed by the PAM.
8. Changes in the Orofacial Myofunctional Evaluation with Scores (OMES).
9. Changes in the IOPI strength and endurance
10. Changes in hyoid position as assessed by a lateral cephalogram
11. Prediction of improvement in SDB severity by objective parameters from a 2D cephalogram obtained at baseline.

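### Secondary endpoint 6 (change in PVT and Stroop) has no planned pre-randomisation session and no fixed end session, so the change can lack an untreated baseline and a common end point.

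*Combined protocol and SAP*

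**What the plan says.** The Outcomes section lists as secondary endpoint 6: "Change in objective daytime functioning testing (PVT and Stroop test". The tests are delivered in the Sleep Well app. Their schedule appears once, in the last paragraph of the Stroop test section: "The completion of the tests will be voluntary in this study", and "Participants will be asked to perform the tests three times during the 90 day study period". No day, window or visit is attached to any of the three sessions.

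Three sections place the 90 days. Baseline evaluation says that, after final inclusion, staff "respectively will schedule the sleep registration and an outcome evaluation session 90 days later". Randomization says "At the end of the baseline consultation participants will be randomized to either OMTa or only auto-monitoring". Section 3.0 calls the 90 days the intervention period and says "The participants will know by default if they are allocated to the OMTa or waiting list with auto-monitoring during the 90-day intervention period".

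Neither test appears in the steps before the baseline consultation, in the baseline assessment list, or in the Outcome evaluation section. The pre-baseline app step concerns the diary: "All participants will receive a standardized information sheet with login information to the electronic sleep diary". The outcome visit repeats the clinical measures, OMES and patient-reported outcomes, and then: "Finally additional repeated diagnostics with the hand dynamometer, chewing test and IOPI will be repeated".

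Section 6.1 compares groups at T1 and T2 without defining either for these tests. Section 6 promises intention-to-treat analysis but gives no rule for skipped tests.

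**The concern.** A change endpoint needs a start value that treatment cannot have influenced and an end value taken at a comparable time in everyone. The plan secures neither for PVT and Stroop. The planned sessions fall after allocation is known, at times left open, so the first value may already contain some effect and the last may precede the full effect.

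Completion is optional among people who know their arm, and staff contact is unequal. Only OMTa participants have, within the 90 days, a start-up session that covers use of the app, a direct link to the study staff, and biweekly video sessions. If more, or different, people complete the tests in one arm, the comparison no longer rests on the randomised groups.

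At stake is the trial's evidence on objective daytime functioning. Test dates can be reported afterwards, but a pre-randomisation value that was never collected cannot be recovered.

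**Working it through.** **Plan's own figure.** The documents give no effect size, uptake or sample size for PVT or Stroop. The only power figure, 26 per group in section 6.2, is for the AHI (two-sided t-test, d = 0.8, 5% level, 80% power). It reproduces: the t-test solution is 25.52, rounded up to 26, with power 80.7%. It says nothing about endpoint 6.

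**Timeline.** Inclusion at the baseline visit, then randomisation at the end of that visit, then 90 days with allocation known, then the outcome visit. Sessions requested within the 90 days are therefore requested after randomisation. No section asks for an earlier one.

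**Effect captured.** Assumption: the effect builds linearly from day 0 to day 90. All test days below are illustrative; none is in the documents. For a first-to-last change, the share captured is (last day − first day)/90. For a between-arm comparison of the last value, it is last day/90. The sample needed for the same power rises by 1/share², if the SD is the same whatever the interval.

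| Test days (first, last) | Contrast | Share | Sample multiple |
|---|---|---|---|
| 1, 90 | change | 89/90 = 99% | 1/0.989² = 1.02 |
| 15, 75 | change | 60/90 = 67% | 1/0.667² = 2.25 |
| 30, 90 | change | 60/90 = 67% | 2.25 |
| –, 75 | last value | 75/90 = 83% | 1/0.833² = 1.44 |

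If the three days were uniformly random over the period, simulation gives a mean first-to-last share of 50% (5th to 95th percentile 14% to 86%). The last test falls on average at day 67.5, so a last-value comparison would capture 67.5/90 = 75%.

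**Selection.** Assumption: the outcome has latent correlation ρ with willingness to complete, and a proportion p completes. The completers' mean is then shifted by ρ × φ(z)/p SD, where φ is the standard normal density and z the cut-off that leaves p above it.

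- p = 75%: 0.318/0.75 = 0.424
- p = 50%: 0.399/0.50 = 0.798
- Difference: 0.374 × ρ

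With ρ from 0.1 to 0.5, 75% completion in one arm and 50% in the other shift the between-arm difference by 0.04 to 0.19 SD with no treatment effect. The direction depends on the sign of ρ and on which arm completes more. With equal completion and equal ρ the shift is zero.

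**The case against.** A reader might infer that the first value is always an on-treatment value and that the change is therefore diluted. The documents do not support that. The text leaves the timing open, and a start, middle and end schedule fits it. After randomisation is also not the same as on treatment: the Description of the intervention has a separate start-up session still to be scheduled, so a test taken soon after the visit could be an untreated value. Participants have app access before baseline, so an early test is possible, although none is requested.

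A second objection concerns the contrast. Section 6.1 compares arms at T1 and at T2, not on change scores. In a T2 comparison a late first test removes nothing; only an early last test does. The 67% share and 2.25-fold multiple belong to a change-score contrast under assumed test days. This limits the size but does not remove the problem: the endpoint is worded as a change, section 6.1 also plans within-group tests and T1-to-T2 effect sizes, and T2 has no window for these tests.

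Third, unequal completion is not shown. The waiting-list arm has the rest of the app and the same technical support, and voluntary testing is a reasonable way to limit burden. That stands, and so selection is a possibility only. The intention-to-treat statement does not settle it without a rule for skipped tests.

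**Conclusion.** The point holds as a gap in the design of one secondary endpoint. No PVT or Stroop session is planned before randomisation, none is fixed at the outcome evaluation, and none is mapped to T1 or T2. Dilution and arm-dependent completion can occur; the documents do not show that they will.

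Their size cannot be fixed from the documents. Under linear accrual it runs from a negligible loss (99% captured) to a third of the effect (67%) for the first-to-last schedules tabulated, with 83% for a last-value comparison at day 75. Haphazard timing could lose more. A faster or slower onset would change all these figures. The AHI endpoint and its sample size are not affected. The change should be made because it is cheap and the missing baseline cannot be recovered later.

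**What to change.** Schedule the first PVT and Stroop session in the diary run-in or at the baseline visit before the envelope is opened, and call it T1. Schedule the last in a fixed window at the outcome evaluation, and call it T2. A mid-period session is optional. Send identical app prompts in both arms.

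In section 6.1, compare T2 between the randomised arms adjusted for the pre-randomisation T1 value, state how skipped sessions are handled, and report completion by arm. Completion can stay voluntary.

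One practical check: the Randomization section puts an e-mail address and password in the envelope, so confirm that the pre-baseline login opens the tests and that its results link to the same participant.

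The cost is protocol wording, app prompts, and a few extra minutes at or before two existing visits.

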### **Description of the intervention**

Participants opening a code unlocking the OMTa treatment module of the application will be given a direct communication link to the PhD students, [name] (Norway) and [name] (Estonia) and two research co-ordinators. [name] and [name] has obtained an Academy of Orofacial Myofunctional Therapy (AOMT) certification diploma. One physical start up session will be scheduled at Ahus and at North Estonia Medical Center. This 60 minute session will be used to instruct participants in OMT exercises and use of the app. All participants will receive a disposable toothbrush and standardized balloons. After that, biweekly video sessions (time 20-30 min) will be scheduled. The exact same amount of sessions and equipment will be offered to the waiting list group after the outcome evaluation. The following exercises are pre-recorded and presented in the treatment module:

#### ***Tongue***

1. Tongue brushing: Brush the superior and lateral surfaces of the tongue while fixing the tongue in different positions of the mouth. Repeat each movement for five times, three times a day for 14 days.
2. Tongue sliding: Place the tip of the tongue against the hard palate behind your upper front teeth. Slide the tongue backwards along hard palate. Repeat 20 times, three times a day.
3. Tongue suction: Suck the entire tongue upwards against your hard palate and press upwards. Both short and long pressure intervals. Repeat 20 times short, 20 times long, three times a day.

4. Tongue down: Force the back of the tongue down against the floor of the mouth. Keep the tip of the tongue in contact with the lower front teeth. Repeat 20 times, three times a day.

### **Soft palate**

1. Elevate soft palate and uvula whilst saying "ah" both intermittently ("a -a -a") and continuously ("aaa"). Repeat 20 times, three times a day.
2. Balloon blow: Inhale through your nose, blow into a balloon with force. Don't take the balloon off your mouth and repeat blowing for five times, three times a day. If socially not acceptable to blow the balloon, blow air through pressed lips five times. Please blow the balloon in the morning and evenings.

### **Facial**

- 1 Put your finger in the oral cavity against your cheek. Pull against your finger with the cheek muscles. Repeat 10 times on each side, three times a day. If socially not acceptable to put the finger in the mouth, blow air from cheek to cheek. Please use finger in the morning and evenings.
- 2 Air pump: Blow air against your cheek while alternating sides. Keep lips closed. Repeat 10 times on each side, three times a day.

The list of exercises is a revised version of the protocol published by Guimaraes et al in 2009 {Guimaraes, 2009, Effects of oropharyngeal exercises on patients with moderate obstructive sleep apnea syndrome@@shared-groups}. Time per set of exercise is 10-15 minutes. The intervention will be ongoing for three months (12 weeks). Progression in exercises, subjective sleep parameters and treatment adherence will be evaluated in video sessions with the PhD students at respective locations. Problems will be solved with joint video sessions with the participant, the PhD student and an experienced OMT therapist.

### **Description of waiting list, auto-management condition**

Participants receiving a code not unlocking the treatment module will have full access to all other parts of the mobile app. After 90 days, during the outcome evaluation, all participants will receive a new code unlocking the treatment module in order to keep outcome evaluators blinded.

## **Outcome evaluation**

At outcome evaluation (estimated time 60 minutes), [name] (Norway) and dr. [name] (Estonia) will repeat the following assessment from the baseline evaluation: A clinical evaluation will consist of height, weight and standardized blood pressure. Thereafter, the quantitative scores (OMES) for assessing the myofunctional therapy and patient reported outcomes will be repeated (see above). Finally additional repeated diagnostics with the hand dynamometer, chewing test and IOPI will be repeated. All data will be collected in the “Redcap” CRF.

Finally, each participants will be given a maximum of five feedback questions. The exact phrasing of the questions will be finalized when answers to similar questions in a pilot study have been analysed. The brief interview will be audio taped and transcribed.

## **Outcomes**

The primary end point of the RCT is change in the AHI

Secondary endpoints:

1. Change in the Epworth Sleepiness scale and PROMs in the European Sleep Questionnaire.
2. OMTa adherence
3. Change in other conventional OSA severity indices (oxygen desaturation index, time below 90% saturation, nadir saturation) and change in novel OSA parameters in SAS identified in the development phase of the project.
4. Change in objective and subjective sleep quality (PSG and sleep diary, respectively).
5. Change in physiological parameters assessed by wearables.
6. Change in objective daytime functioning testing (PVT and Stroop test).
7. Change in self-reported self-efficacy as assessed by the PAM.
8. Changes in the Orofacial Myofunctional Evaluation with Scores (OMES).
9. Changes in the IOPI strength and endurance
10. Changes in hyoid position as assessed by a lateral cephalogram
11. Prediction of improvement in SDB severity by objective parameters from a 2D cephalogram obtained at baseline.

## **5 Procedures**

### ***5.1: Responsibility***

Participants of the study will be transferred from regular clinical practice to the research project for 90 days. During this period, the national project leader is medically responsible. Breaches of the protocol will be systematically addressed and reported to a hospital appointed monitor at the division of surgery. After the 90 days outcome evaluation, all participants will be allocated to an open label follow-up condition. The frequency of follow-up consultations is dependent on future funding. During follow-up, participants of the waiting list, auto-management condition will be offered up to 10 video recordings free of charge with the PhD student. All participants will have unlimited access to the auto-monitoring platform and the intervention module during follow-up.

